Determination of eligibility: Participants in the full intervention (350 women) will be screened for eligibility by the CO-I or a local study coordinator. The Co-I/local study coordinator will administer a brief screening questionnaire prior to obtaining informed consent (Appendix A). The screening questionnaire will cover the inclusion/exclusion criteria listed above. For women who screen potentially eligible, the CO-I/local study coordinator will further describe the study. Eligible potential participants will be told that we are conducting a research study to understand how new innovations like an at-home HPV self-sampling tool would be accepted by you and in your community. The study will involve completion of a baseline survey (Appendix B) about their sexual and reproductive practices and cervical self-sampling.

In our research, we plan to use a self-sampling device developed by Preventive Oncology International (POI) and the National Institutes of Health (NIH). The POI/NIH self-sampler is considered a non-significant risk device and has been approved for research conducted by NIH faculty throughout the United States and in various international settings. This device is manufactured by Puritan Medical Products, and is thought to reflect an improvement over other self-samplers, given a larger Collection Swab tip, which enables a woman to collect cells from more of

the cervix's total surface area with less effort. The POI/NIH self-sampler is a 20 cm in diameter, which is similar to a regular-sized tampon. This sampler is easy to use. A woman inserts the device into her vagina until she feels slight resistance. The participant then holds the paddle end of the Collection Swab and rotates it five times. She then withdraws the Collection Swab. Once the Collection Swab is fully removed from the vagina, the participant places the Collection Swab into liquid cell preservative and rotates it five times. The participant can then dispose of the swab in a household trash can and secure the vial lid. The participant should return the vial by mail (she will be provided a pre-addressed, stamped envelope) or in person to a specified return location. The CO-I/local study coordinator will be responsible for storing and shipment of the samples to the SCCC for testing.

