Participants will receive the HPV self-sampler at the time they complete the baseline survey with the Co-I/local study coordinator. The HPV self-sampler kit will include the collection swab and the vial for collecting and storing the specimen, and an instructional sheet that visually depicts the steps for self-sampling. 115 women will receive a culturally-targeted, fear appeal message for the HPV self-sampler kit; 115 women will receive only a fear appeal message, not targeted for the Jamaican populace; and 115 women will receive only the self-sampler tool with no message appeal (plain packaging). (Appendix G & J). The Co-I/local study coordinator will offer the HPV self-sampler accompanied by an instruction sheet on how to use the self-sampler. At this point participants will receive some sensitization on the topic, which will include: 1) health education on the importance of cervical cancer screening using a short intervention/educational script (Appendix H) and 2) motivation to encourage women to have screening using the HPV self-sampler. Women will also be informed of the following: 1) HPV infection usually is not detectable or harmful; 2) nearly everyone who has had sexual intercourse has been exposed to HPV and infection is very common; 3) a positive HPV test result does not indicate the presence of cancer and that not all women who test positive for an HPV infection will not develop advanced cancer. It will also be stressed to women that if they have not seen a doctor recently they will still need to see a provider to address other health issues, which may include a gynecologic exam. They will also be advised that if HPV obtained through self-sampling is positive, they will need follow-up medical care at clinical sites (a list of possible sites will be provided). and to package and return it by mail or to the address provided. A brief survey on intentions will then be administered (Appendix K). Participants will be asked to use the tool at home by following the instructions, The local study coordinator will follow up with participants who do not return the kit within 1 week via SMS messaging. All participants will receive the following message: "Please remember to return your HPV self-sampler kit to X location during the following times: X Y, and Z. Please ignore this message if you have already returned the kit. Thank you."

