There are psychological risks associated with receiving an abnormal test result from self-sampling. Participants may interpret an abnormal result as a diagnosis of cancer rather than an infection with HPV. The participant may feel hopeless in response to an abnormal result, believing that there is nothing that can help. As a member of an underserved group she may feel that adequate health services are not available or accessible to her. She may also feel guilty that she has done something wrong or someone has wished ill health upon her. She may feel embarrassed to tell her friends, family, and other ones, fearful of how they may judge her and reflect upon her diagnosis.

If the participant decides that they do not wish to participate in the study after it has started, they will be advised to tell the Co-I or local study coordinator. They will be advised that there is no penalty imposed if they decide to end their participation early and/or refuse to answer any question.

Adverse Experience Reporting: If any participant who chooses to use the HPV self-sampler indicates to the local study coordinator or Co-I that a discomfort is persistent or something else has occurred, the Co-I should contact directly the Principal Investigator and oversight committee of the study. Participants who experience any adverse effect or study-related injury will be navigated to appropriate follow-up care with our community partners and/or The Ministry of Health Jamaica immediately for follow-up care.

16) Potential Benefits to Subjects*

A potential benefit for all participants is the opportunity to be screened. There are no other direct benefits to participants from taking part in the study.

17) Vulnerable Populations*

This research does not involve individuals who are vulnerable to coercion or undue influence or vulnerable populations.

18) Multi-Site Research*

N/A

19) Community-Based Participatory Research*

This project shares some elements of community-engaged research. Firstly, the community will be involved in the conduct of the study as participants, to improve the utilization of local knowledge in the development of an effective intervention or program at a national level. Secondly, we will collaborate with local institutions to plan the research project and for assistance in the recruitment of participants.

20) Sharing of Results with Subjects*

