Participants will be informed that they do not have to answer a question if they do not want to. They are also allowed to withdraw from the study at any moment. All correspondence with participants will be by direct contact. All electronic surveys

and forms will be entered and uploaded using Research Electronic Data Capture (REDCap), which is securely hosted by the University of Miami's IT Department.

To protect the study's subjects' privacy interests, interviews with participants will take place in a location that offers enough privacy, so that they do not have to worry about being seen entering a place that they feel might stigmatize them, or about being overheard when answering sensitive questions or discussing private medical information with other than their physicians or gynecologists. To make the participants more comfortable with the research, the data collection will be limited to only the minimum amount of information necessary to accomplish the study's purposes. Moreover, the questions will be asked by female researchers to make the subjects feel at ease with the situation.

28) Compensation for Research-Related Injury

All research involves a risk of research-related harm to participants. While we do not expect any physical injury related to this study, we may encounter psychological, social or economic risks, in spite of all safety measures. If such problems occur, the researchers will refer participants to the resources of the Ministry of Health for further care and attention. The University of Miami has not set aside funds to pay for any such reactions, or for any related care.

29) Economic Burden to Subjects

The subjects may be responsible for the local transportation expenses related to arriving to the research locations. Refreshments will be provided for the focus group participants.

30) Consent Process

Written Informed consent will be obtained by the Co-I/local study coordinator after pre-screening. Consent will be obtained in a private area from individuals who are eligible and agree to participate after the Co-I/local study coordinator describes the study. Potential participants will be told that we are conducting a research study to understand how innovations like an hpv self-sampling tool would be accepted by you and in your community.

Participants are given the opportunity to opt out of selected study procedures. Informed consent will be provided in English.

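### The scripted reminder SMS names HPV, a disclosure that the privacy section does not address, and omits the mail return route that Section 10 offers

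*Combined protocol and SAP*

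**What the plan says.** Section 10 (Collection of Self-Samples) sets the trigger for the reminder: "The local study coordinator will follow up with participants who do not return the kit within 1 week via SMS messaging". The next sentence introduces the script with the words "All participants will receive the following message", and the script reads "Please remember to return your HPV self-sampler kit to X location during the following times: X Y, and Z". The place and hours are placeholders; the rest of the wording is fixed. A closing line tells women who have already sent the kit back to disregard the message.

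Earlier in the same section the return routes are given as "The participant should return the vial by mail (she will be provided a pre-addressed, stamped envelope) or in person to a specified return location". The counselling text at kit hand-out repeats both routes. Section 20 (Sharing of Results with Subjects) mentions mail alone.

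On privacy, Section 27 says "All correspondence with participants will be by direct contact" and does not define the term. It promises interview venues private enough that women need not worry about "being seen entering a place that they feel might stigmatize them". It does not mention text messages. Section 4 (Background) lists privacy concerns among the factors that keep Jamaican women from screening, and cites privacy as an issue that self-sampling addresses.

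**The concern.** A text message can be seen by someone other than its recipient. One that names an HPV self-sampler tells that person that the woman is being tested for HPV, and where and when she is expected. Section 10 itself links HPV to sexual intercourse in what women are told at counselling. The reminder works just as well without the term. In a study of women for whom privacy is a stated barrier, the disclosure is avoidable.

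The second issue is practical and needs no view about stigma. The script points to a place with hours, which fits drop-off only. A woman who still holds the stamped envelope could take it that mailing is no longer an option. The message goes to women whose return is still open, and Section 9 makes return of the sample by a majority of women the first of its two success conditions. The reminder should therefore give the full return instruction.

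**Working it through.** No arithmetic applies. The check sets the texts side by side.

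1. **Does the script name HPV?** Yes. The term is in the fixed part of the wording in Section 10, not in a placeholder.

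2. **Does the reminder need the term?** No. Its job is to prompt return of something the woman already has, and a neutral phrase such as *study kit* identifies it.

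3. **Does the script match the return routes?** Not fully.
   - Section 10, device description: mail in the envelope supplied, or in person.
   - Section 10, counselling text: mail, or the address given.
   - Section 20: mail only.
   - Scripted SMS: one place, with hours.

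   The SMS is the only one of the four that leaves mail out. The four texts need to be reconciled.

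4. **Does Section 27 cover the content of a text message?** No. The sentence about being seen entering a place is about where interviews are held. The correspondence sentence uses an undefined term that neither admits nor excludes SMS. Nothing in the section deals with message content, shared phones or other readers.

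5. **Does the risk section name this harm?** Not as such. Section 15 says "She may feel embarrassed to tell her friends, family, and other ones, fearful of how they may judge her", but the sentence goes on to her diagnosis, and its paragraph opens with the psychological risks of an abnormal result. The reminder carries no result and is sent while the kit is still outstanding. The passage shows that the protocol treats HPV findings as sensitive, but it does not identify a reminder risk.

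6. **Who receives the SMS?** The trigger sentence limits it to women who have not returned the kit at one week; the next sentence refers to all participants. The likelier reading is that every woman followed up gets the same words. The closing line about disregarding the message fits kits in transit and does not settle the matter.

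7. **Could the wording bias the comparison of arms?** No. One script serves all three message conditions.

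**The case against.** The strongest case against the point is that it is a preference about wording. Women hear of both routes when they receive the kit and are given the envelope. The success condition in Section 9 refers to return as the toolkit instructs, not as the SMS does. Nothing in the documents shows that other people read participants' texts or that this wording would discourage return. Privacy in Section 4 is a background barrier to screening, listed beside fear of pain and not knowing where to be tested; it is not a statement about phones. All of this stands, and it keeps the point small. It does not explain why the script should name HPV or leave out a route that the protocol offers.

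A reader might go further and infer that the SMS breaches Section 27 and realises a harm named in Section 15. The documents do not support that. The venue sentence governs interviews, the named embarrassment follows an abnormal result, and direct contact can reasonably include a text from the coordinator, since the protocol already plans posttest and results contact by telephone. A reader might also infer that women have not agreed to SMS contact. The consent form is not in the reviewed text, so its absence there shows nothing.

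**Conclusion.** The point holds as a low-cost improvement. Followed as written, the script discloses more than a reminder requires, on a matter that Section 27 leaves unaddressed, and gives an incomplete return instruction to women whose return counts toward the Section 9 success condition. It is in tension with the protocol's privacy aims without directly contradicting any provision.

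Its size cannot be stated. The documents give no expected return at one week, so the number of recipients is unknown, and there is nothing from which to estimate how often a message would be seen by others or how the wording would affect return. The conclusion assumes only that the script is sent as worded and that both return routes are meant to remain open.

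**What to change.** - Replace the script with neutral text that gives both routes, for example: *Please remember to return your study kit by mail in the envelope provided or at X during these times.* Keep the closing line for women who have already returned the kit.
- State in Section 10 that the message goes to all women whose kit is not logged as returned at one week, in place of the unqualified reference to all participants.
- Bring the return routes in Sections 10 and 20 into line with each other and with the SMS.
- State in Section 27 that SMS is used, and confirm that the consent form covers it.

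The cost is one reworded message and a few clarified sentences. The reminder keeps its function and timing, and neither the comparison of arms nor the analysis changes.

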Jamaican women will be recruited for participation in two different phases of this research project. Efforts will be made to include women from rural areas, urban areas, and varying socio economic and cultural backgrounds. Recruitment will occur in three identified low-screening regions in Jamaica (using national statistical data on screening rates per parish in Jamaica), and enrolment will take place through local community organizations as well as at community events such as health fairs.

8) Study Timelines*

An individual subject in the research is expected to participate up to maximum of 4 months. Enrolling study subjects is expected to not exceed one month prior to the actual study date. The estimated date for the investigators to complete this study is September 30, 2018. The primary data analysis will be completed by October 31, 2018. Other studies that have utilized community and government partners have been successful at recruiting a similar number of participants over a short time. For example (Barrett & Huffman, 2011) collected their entire dataset in 3 weeks in October 2007 (276 Jamaican adolescents). Another example is (Lewis-Bell et al., 2013), a cross-sectional study that

took place in April–July 2010 with 852 sexually-active Jamaican women, 16–49 years of age.

9) Study Endpoints*

The primary study endpoints are:

- Development of messages and design of HPV self-sampling tool kit.

Based on formative results from interviews (see Appendix C for interview script), messages will be designed that are culturally appropriate and tailored for any audience segments which emerge from the data. Feedback will be used to design a culturally adapted HPV DNA self- sampling toolkit for this context.

- Evaluation of culturally-tailored HPV DNA self-sampling toolkit.

Enrolled participants will complete a pre-test/baseline questionnaire which will be based on the theoretical constructs identified, and which will also be assessed in the posttest. The intervention will be considered a success when: 1) the majority of women targeted opt to return their sample, as instructed on the toolkit, for testing and, 2) upon evaluation (posttest - See Appendix C), women report higher levels of, knowledge, self-efficacy and response efficacy or positive changes in attitudes toward screening than at baseline.

10) Procedures Involved*

Interviews

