Posttest Interview: All participants will be asked to complete a posttest survey which may be administered by phone or in person, if convenient (Appendix D) upon return of the self-sampler kit.

Compensation: All participants will be provided a one-time small incentive of approximately \$21USD (\$2,500 Jamaican dollars) immediately upon completion of the narrative interviews (for the interview participants), and upon completion of the posttest interviews (for the message design experiment participants).

Report of HPV Lab Results: The Co-I will receive test results from lab and provide information to the local study coordinator. The Co-I/local study coordinator will call participants within 4-6 weeks to notify them of their test results when they are received.

Participants who test negative will be encouraged to follow-up with their doctor and rescreen in 36 months, based on the US Preventive Services Task Force (USPSTF) guidelines. Participants whose test results indicate insufficient sample (insufficient cellular quantity for analysis) would be asked if they had a hysterectomy. If no, the participant will have the option of providing a second sample if they are located within reasonable distance from a local project partner, and an appointment will be scheduled by Co-I/local study coordinator to either deliver the kit or for the participant to pick up. Participants who test positive for HPV will be navigated to appropriate follow-up care with our community partners and/or The Ministry of Health Jamaica within 30 days of receiving the result. The Co-I will work with Ministry of Health staff to ensure that women with abnormal findings receive timely follow up. The Co-I/local study coordinator will follow up with participants who do not return the kit within 30 days.

For individuals who screen eligible but declined consent/enrollment, the brief demographic information collected during the eligibility screen (age, ethnicity) will be kept without any identifiable information so that we may compare responders versus non-responders. For individuals who choose to participate in the study, the CO-I/local study coordinator will obtain consent (see Appendix F), complete the baseline survey (Appendix B) and give the self-sampling tool (or schedule a time to do so at a time or location convenient for the participant).

11) Data and Specimen Banking*

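### The posttest is timed only to kit return and no planned contact is said to deliver it to non-returners, so changes from baseline may be observed mainly in women who returned a kit

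*Combined protocol and SAP*

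**What the plan says.** Section 10, Posttest Interview, puts everyone in scope: "All participants will be asked to complete a posttest survey which may be administered by phone or in person, if convenient". The same sentence supplies the only timing: "administered by phone or in person, if convenient (Appendix D) upon return of the self-sampler kit". No section gives a date, a window or a fallback occasion for a woman who never returns her kit, and no handling of missing posttests is described.

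The Compensation paragraph of section 10 has the same structure. It promises payment to all ("All participants will be provided a one-time small incentive") but ties it to an event, "upon completion of the posttest interviews (for the message design experiment participants").

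Section 9 sets two conditions for success. The first is that "the majority of women targeted opt to return their sample". The second is that "women report higher levels of, knowledge, self-efficacy and response efficacy or positive changes in attitudes toward screening than at baseline", judged at the posttest. Section 12 then uses change in knowledge, attitudes and perceived efficacy as mediators of change in screening outcomes, a term it does not define.

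Section 9 cites Appendix C for the posttest and section 10 cites Appendix D. Neither appendix is in the text reviewed.

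**The concern.** A coordinator who follows section 10 knows when to survey a woman who hands in or mails a kit, but has no instruction for a woman who does neither. Whether criterion 2 is measured would then depend on kit return, which is criterion 1. One outcome would select the sample for the other.

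Women whose knowledge or confidence rose may also be the ones more likely to return a kit. If so, the average gain among returners is larger than the gain in all enrolled women, and criterion 2 looks better than it is. A posttest that was never taken cannot be recovered by analysis afterwards.

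The mediation analysis is exposed as well, because its mediators are the same change scores.

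**Working it through.** **1. Does any planned contact reach non-returners with the posttest?**

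- Section 10, text message to women who have not returned the kit within a week: its wording is printed in full and is a return reminder only.
- Section 10, follow-up tied to 30 days: no content is stated, and the sentence can mean follow-up within 30 days or follow-up of women who have not returned by day 30.
- Section 20, call to non-returners: it appears under sharing of results, with no date and no mention of a survey.
- Section 13, phone call for evaluation: it is mentioned only as a data-entry setting, with no time and no recipients.

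None is said to deliver the posttest. The last two could do so, but the plan does not make the link.

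**2. How many women could be affected while criterion 1 is still met?**

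Inputs: three groups of 115 (section 10), so 3 × 115 = 345; enrolment target 350 (sections 6 and 24); criterion 1 is a majority returning (section 9). The smallest majority is floor(n/2) + 1.

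- n = 345: 172 + 1 = 173 returners, leaving 172 (172/345 = 49.9%).
- n = 350: 175 + 1 = 176 returners, leaving 174 (174/350 = 49.7%).
- One arm of 115, if each arm just passes: 57 + 1 = 58 returners, leaving 57 (57/115 = 49.6%).

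These are the largest non-return counts compatible with meeting criterion 1. If criterion 1 fails, the number is larger. At an assumed 80% return (276 of 345) it is 69.

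**3. How would a gain among returners differ from the gain in all women?**

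Let r be the return proportion, and m_R and m_N the mean changes in returners and non-returners. The mean change in all women is r·m_R + (1 − r)·m_N. If only returners are surveyed, the observed change is m_R, so

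overstatement = (1 − r)(m_R − m_N).

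The documents give neither r nor the difference. As an illustration, assume that returners gain 0.5 SD and non-returners gain nothing:

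- r = 50%: observed 0.50 SD, all women 0.25 SD.
- r = 65%: observed 0.50 SD, all women 0.325 SD.
- r = 80%: observed 0.50 SD, all women 0.40 SD.
- r = 90%: observed 0.50 SD, all women 0.45 SD.

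The overstatement is zero if the two groups change equally, and it reverses if non-returners gain more.

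**4. Is this mainly a loss of precision?**

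No. At an assumed two-sided 5% level and 80% power, the detectable paired change is (1.960 + 0.842)/√n. That is 0.150 SD at n = 350 and 0.212 SD at n = 175. Halving the sample costs little beside the possible selection effect.

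**5. Mediation.**

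If screening outcomes in section 12 means kit return, and only returners have mediator change scores, the outcome equals 1 for every woman analysed. Its variance is zero. A fitted slope would be 0 by construction and would say nothing about mediation.

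**6. Criterion 1.**

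Section 11 labels each specimen with the number assigned at intake, so return can be counted for every enrolled woman without a posttest.

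**The case against.** The best reply is that the plan already intends to survey everyone. Both the posttest sentence and the compensation sentence begin with all participants, and payment on posttest completion presupposes a posttest for each woman. Section 9 equates evaluation with the posttest, so the phone call for evaluation in section 13 is naturally the posttest call. Section 20 has non-returners called, and phone administration is allowed. The posttest sentence can also be read so that kit return governs only the in-person option. An appendix might contain a schedule.

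This stands as evidence of intent, and a reader should not infer that the plan deliberately excludes non-returners. It does not supply an occasion: none of these places says when, or on which contact, a non-returner is surveyed. If an appendix does say so, a cross-reference settles the point.

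Section 10 also gives an intentions survey (Appendix K) at kit hand-out, independent of return. It is useful post-exposure information, but it is not said to measure knowledge or efficacy, so it does not replace the posttest.

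Three stronger inferences are tempting but not supported:

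- That half the posttests will be missing. The 49.9% is a ceiling given that criterion 1 is met; no return rate is stated.
- That criterion 2 needs a majority of women to improve. The word majority in section 9 belongs to criterion 1 only.
- That comparisons between arms are biased. H1 in section 3 expects better results with the tailored message, and comparing arms among returners would select on a behaviour the message aims to change. But section 12 names no between-arm test, so this is conditional.

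The mediation point is conditional too. Section 12 speaks of changes in screening outcomes under a within-subject approach, and kit return has no baseline value from which to change.

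**Conclusion.** The point holds as a gap in the assessment schedule with a selection consequence, and it should be fixed. Applied literally, section 10 observes the criterion 2 changes and the mediators only, or mainly, in women who returned a kit. Up to 172 of 345 women (174 of 350) could have no stated posttest occasion with criterion 1 still met.

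Any overstatement of the gain depends on a return rate and on a returner/non-returner difference that the documents do not give, so the SD figures show a mechanism and are not an estimate for this trial. Criterion 1 itself is not affected.

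Confidence is medium, because the wording points to an intent to survey everyone and the appendices could not be read.

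**What to change.** State in section 10 that the posttest is given to every enrolled woman regardless of kit return, and that non-returners are surveyed by phone on the call already planned in section 20. Give that call a date; section 8 sets the limit ("An individual subject in the research is expected to participate up to maximum of 4 months"). State that the incentive is paid on posttest completion whether or not a kit came back. Align the appendix references in sections 9 and 10.

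Record the posttest date relative to kit hand-out, kit return and result disclosure. Report posttest completion and change scores by arm and by return status. Count return from the specimen log for all women, separating kits returned before and after the posttest contact.

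Cost: a short text change, some extra phone time, and about US$21 per non-returner. That is 172 × 21 = US$3,612 at the ceiling, or 69 × 21 = US$1,449 at an assumed 80% return, and the payment is already promised to all participants. Two downsides remain. Non-returners are surveyed at a different time from returners, which should be reported as a limitation. The call may also itself prompt some returns, which is why returns before and after it should be shown separately.

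A single posttest window for all women, counted from hand-out, would remove the timing difference but is optional. It could also prompt returns, it would place some posttests before the device is used, and it might lose some returners who would have been surveyed at hand-in.
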